3.4 Safety Objectives

The safety objectives of the study are to monitor and assure safety of all participants during and after the Experimental Sessions by assessing physiological effects, psychological distress, SAEs, medical events, spontaneously reported reactions, and suicidal ideation and behavior. All of the objectives below will be assessed in both participants.

- Suicidal ideation and behavior will be assessed with the Columbia Suicide Severity Rating Scale (C-SSRS) according to the Table 3: Time and Events.
- During Experimental Sessions, Subjective Units of Distress (SUD) and vital signs including blood pressure, heart rate, and temperature will be collected.
- Serious Adverse Events (SAEs) will be collected in both groups through Study Termination. All Adverse Events (AEs) will be collected on the day of drug administration through the Primary Endpoint and will be followed to resolution.
- Any spontaneously reported reactions will be collected from the day of the Experimental Session through seven days after both Experimental Sessions. Reactions that have not resolved to the participants' Baseline level of severity after seven days will be collected on the Adverse Event Report page until resolution.
- Assess General Wellbeing (clinician-rated) at all visits and phone calls for both the participants.
- AEs requiring medical attention will be collected through Study Termination.
- Events related to planned treatments or physician visits for Baseline conditions collected in the Medical History will not be collected unless there is an exacerbation of the condition.
- Any AE leading to withdrawal from the protocol will be collected throughout the study.
- All AEs related to changes in psychiatric status will be collected throughout the study.
- Baseline medications and changes to psychiatric medications will be collected throughout the study.
- Changes in pre-existing chronic pain and/or tinnitus symptoms will be collected throughout the study using a Visual Analog Scale in any members of the dyad reporting these symptoms.

4.0 Protocol Design

This is a Phase 1/2 open-label study in 10 dyads including a participant who has been diagnosed with PTSD for at least 6 months (PTSD+ participant) and a CSO participant (i.e., intimate or non-intimate person who does not have a current diagnosis of PTSD). At screening, both members of the dyad will sign separate informed consents. Both must give written informed consent in order for the dyad to be enrolled. Dyads must consist of

people who are in a significant ongoing relationship, including but not limited to romantic relationships. Baseline screening procedures and assessments will be conducted for both members of the dyad. Dyads in which both members meet all Inclusion and no Exclusion Criteria will be enrolled.

Eligible and enrolled participants will undergo a 2-month course of psychotherapy as a dyad that includes CBCT for PTSD integrated with MDMA-assisted psychotherapy. The CBCT sessions, as described in Monson and Fredman's (2012) manual [1], will be integrated with elements of the Treatment Manual for MDMA-assisted Psychotherapy [2] in order to modify CBCT to incorporate MDMA as a catalyst for the therapeutic process. Sessions will be conducted by a co-therapy team and will include Preparatory Sessions, two Experimental Sessions of MDMA plus psychotherapy, and non-drug CBCT psychotherapy Integrative Sessions. The primary objective is to measure changes in PTSD symptoms via CAPS global severity scores in PTSD+ participants at Baseline and the Primary Endpoint, one month after the 15th CBCT session. Additional measures evaluate various qualities of the relationship between the participants.

The Experimental Sessions will last 6 to 8 hours and will be scheduled 3 weeks apart, with an intervening course of non-drug therapy. The non-drug psychotherapy includes two Preparatory Sessions prior to the first Experimental Session and five Integrative Sessions after each Experimental Session. Integration visits will be conducted by telemedicine (video conferencing whenever possible, telephone if there are occasions when video conferencing is not technically possible) and will include both members of the dyad. The sessions will follow a combination of the MDMA-assisted psychotherapy manual and the CBCT manual, with each method modified as needed to combine the therapies.

Table 3: Time and Events

	Screen	Preparat	tory	Experimental Session 1, Integrative Sessions Midpoint Experimental Session 2, Inte					Integrative	e Sessions		Primary Assess	3 Mo LTFU	6 Mo LTFU					
Visit #	Pre-Study	V 1	V 2	V3	V 4	V 5	V6	V 7	V 8	V9	V10	V11	V12	V13	V14	V15	V16	V17	V18
Type of Session	Screening	Prep	Prep	Exp	Int	Int	Int	Int	Int	Assess /Prep	Exp	Int	Int	Int	Int	Int	Outcome	Assess	Assess
Visit Format	Telemed or Visit	Telemed	Visit	Visit (overnight)	Visit	Telemed	Telemed	Telemed	Telemed	Visit	Visit (overnight)	Visit	Telemed	Telemed	Telemed	Telemed	Telemed	Telemed	Telemed
Visit Timing Window	>1 day, month prior to Visit 1	≤ 1 Mo before V2 ^J	Day 0	Day 1	Day2	over 3 w	4 vis eeks betw		nd V10	~3 weeks post V3; prior to V10	~3 weeks post V3	1 day post V10	over 4	4 v weeks betv	risits veen V10	and V15	1 Mo post V15	3 Mo post V15	6 Mo post V15
CBCT Manual Session #			1, 2, 3	4, 5 – Condensed delivery just after MDMA administration	Review	6	7	8	9	10, 11	Review	Review	12	13	14	15			
Initial Phone Screen	✓																		
Informed Consent	✓																		
Medical/Psychiatric History (Medical Record Review)	✓																		
General Phys. Exam (BP, Pulse, Temp)	✓A																		
Brief Neurological Exam	✓																		
ECG	✓																		
SCID-RV	✓																		
Clinical Lab Tests, w/ HIV, HCV test	✓A																		
Collect Concomitant Medication	✓	✓	✓	✓	✓	✓	✓	✓	✓	✓	✓	✓	✓	✓	✓	✓	✓	✓	
Medication Taper (if applicable)		✓																	
Study Enrollment after meeting I/E		✓	✓																
Record to Audio/Video		✓	✓	✓	✓	✓	✓	✓	✓	✓	✓	✓	✓	✓	✓	✓	✓	✓	
Drug Screen	✓A			✓							✓								
Pregnancy Screen (if applicable)	✓A			✓							✓								
Administer IP Drug + Therapy/CBCT				✓							✓								
Integrative Session					✓	✓	✓	✓	✓			✓	✓	√	✓	✓			
Issue Out of Session Assignments				✓	✓	✓	✓	✓	✓		✓	✓	✓	√	✓				
7 days of Telephone Contact					✓ G	✓ G	✓ G					✓ G	✓ G	✓ G					
CAPS ^I	✓																✓	✓	✓
PCL individual and participant	✓		✓		✓	✓	~	√	√	√		✓	✓	✓	√	✓	✓	✓	✓
BDI-II	✓									✓							✓	✓	✓
IRI	✓				✓					✓		✓				Ī	✓	✓	✓
General Wellbeing	✓	✓	✓	✓	✓	✓	✓	✓	✓	✓	✓	✓	✓	✓	✓	✓	✓	✓	✓
TAS-20, QRI, SORTS, CTS-2, IPF, MSIS, TABS, MDI, ERQ, PSQI, PTGI, CSI	√									√							✓	√	√
LTFU Questionnaire																		✓	✓
IPC	✓			✓C						✓	✓C						✓	✓	✓
RRPQ																	✓		
Vitals (Monitoring of BP, Pulse and Temp)				✓							✓								
Changes in Tinnitus and/or Pain H	✓	✓ D	✓ D	✓ D	✓ D	✓ D	✓ D	✓ D	✓ D	✓	✓ D	✓ D	✓ D	✓ D	✓ D	✓ D	✓	✓	✓
Subjective Units of Distress				✓							✓								
C-SSRS	✓		✓F	✓ B, C, D	✓					✓	✓ B, C, D	✓					✓	✓	✓
SAEs, AEs of psychiatric status or withdrawal		✓	✓	✓	✓	✓	✓	✓	✓	✓	✓	✓	✓	✓	✓	✓	✓	✓	✓
AEs Requiring Medical Attention				✓	✓	✓	✓	✓	✓	✓	✓	✓	✓	✓	✓	✓	✓	✓	✓
Spontaneously Reported Reactions				✓	✓	✓	✓				✓	✓	✓	✓					
All AEs		✓	✓	✓	✓	✓	✓	✓	✓	✓	✓	✓	✓	✓	✓	✓	✓		

- A = Performed locally.
- B = At the beginning of the session.
- C = Approximately 6 hours after administration of MDMA.
- D = As needed.
- E = Approximately every 60 minutes.
- F = Given after medication washout.
- G = For 7 days after Experimental Session, contact will be made by phone or telemedicine and not both, C-SSRS D2 and D7 of calls only, General Wellbeing for all 7 days.
- H = Only in participants with pre-existing chronic pain or tinnitus.
- I = CAPS may be recorded to video.
- J = Additional time allowed if necessary for medication tapering.

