5.1.2 Safety Measures

Safety measures will be applied as described below to minimize risks associated with drug-assisted psychotherapy sessions. The therapists or study physician will be available via mobile phone or pager throughout the study to ensure participant safety. At least one member of each therapy team will maintain Basic Life Support (BLS) certification.

Safety measures, including vital signs and a measurement of psychological distress, will be assessed during all Experimental Sessions. Participants will rate their current degree of subjective distress with the SUD scale, which is a single-item self-report scale. The SUD will be completed repeatedly during the Experimental Sessions, with the degree of distress marked along seven points. Results of the SUD are intended to assist therapists in maintaining participant safety during Experimental Sessions. Both the PTSD+ participant and the CSO participant will complete the SUD according to the Measures and Time and Events Table.

The C-SSRS is a clinician-administered measure of suicidal behavior devised to detect potential suicidal thoughts or behaviors during a clinical trial [171]. It consists of a "Baseline" form that assesses lifetime suicidal ideation, ideation intensity, and behavior and a form for assessing current suicidal ideation and behavior. The C-SSRS consists of a

series of questions, and can be administered during a face-to-face interview or over the telephone. Suicidal ideation and behavior will be assessed at Baseline, during most face-to-face visits, during the second and seventh days of telephone contact, and after each Experimental Session. Participants who are discontinuing medication to participate in the study will complete the C-SSRS before and after medication washout. The C-SSRS Intensity scale for Lifetime obtained a Cronbach's alpha of 0.93 and 0.94 for the Since Last Visit form, and Last Visit C-SSRS severity scores were positively correlated with the BDI "suicide thoughts" item [172]. Both the PTSD+ participant and the CSO participant will complete the C-SSRS according to the Measures and Time and Events Table

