a. Explain and obtain written informed consent from the PTSD+ participant and CSO participant. Written informed consent must be obtained prior to performing any tests or evaluations for the study

- b. Assign the dyad a screening number. Complete the Screening Log
- c. Review the ability of participants of childbearing potential to become pregnant and their commitment to practice appropriate birth control as determined by the Clinical Investigator for the treatment period of the study
- d. Qualified study staff will obtain medical and psychological history by interview for both the PTSD+ participant and CSO participant
- e. Qualified study staff will administer the lifetime C-SSRS at baseline to assess suicide risk for both the PTSD+ participant and CSO participant
- f. General Wellbeing will be assessed for both the PTSD+ participant and CSO participant.
- g. Qualified study staff will collect information on pre-study and current medications for both the PTSD+ participant and CSO participant
- h. A physician will perform a general physical examination for both the PTSD+ participant and CSO participant. The examination will involve the following procedures:
 - Blood pressure
 - Pulse
 - Height
 - Weight
 - Body temperature
 - Examination of head, eyes, ears, nose, throat, skin, heart, lungs, abdomen, and extremities
 - Brief neurological exam (cranial nerves 2-12, sensory, motor, reflexes and cerebellar function)
 - Electrocardiogram (ECG)
 - Serum electrolytes, metabolic profile, urinalysis and complete blood count
 - Thyroid stimulating hormone (TSH), free T3 and free T4
 - Human Immunodeficiency Virus (HIV) serology
 - Urine-dip pregnancy test on females with childbearing potential
 - Urinary drug test.

Results of HIV serology will be kept confidential, and appropriate referral for counseling may be necessary in accordance with state law. The clinical laboratory values will be used to establish eligibility and will be kept with the participant's source record. The clinical laboratory values will not be captured in the CRF, but will be used to establish eligibility and will be kept with the participant's source record. Clinically significant abnormal values will be captured as medical history. If, upon examination, there are questions raised about possible medical problems, the study physician will request a review of participant medical records and request additional tests or assessments as indicated.

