5.2.2 Preparatory Psychotherapy Session (Visit 1 - Telemedicine Visit)

(Less than 4 weeks prior to Visit 2)

Participants who do not complete all screening activities will not be enrolled. Eligibility may be discussed by phone after screening is complete and at the time Visit 1 is scheduled but the final confirmation will occur at Visit 1. If all Inclusion Criteria and no Exclusion Criteria are met, eligibility will be confirmed with the participant.

- a. Complete a final review of Inclusion and Exclusion Criteria
- b. Assess General Wellbeing
- c. Confirm eligibility and willingness to participate in study
- d. Enroll participant and issue dyad number
- e. Ensure medical history and medication history is complete. After enrollment new events will be collected as AEs and new medications, as described in Sections 8.0 and 9.0.
- f. Discuss medication tapering, if applicable. Upon confirmation of eligibility, the PI or another designated study physician will consult the prescribing physician to initiate medication tapering for the PTSD+ participant and the CSO participant, if applicable, who must refrain from taking a psychiatric medication for the study. The prescribing physician's opinion about medication discontinuation will documented either in writing from the prescribing physician, or in writing by the study physician documenting phone contact with the prescribing physician. Tapering will follow a time course appropriate for the medication given its half-life, with the first Experimental Session scheduled to occur after complete washout. Individuals using opiates for pain management will be asked to decrease the dose or avoid taking their pain medication for 24 hours prior to Experimental Sessions if possible, as these medications may reduce the efficacy of MDMA. Participants will be permitted to take their prescribed opiate medication during this period if necessitated by pain flare-ups.

This first Preparatory Session will last 90 minutes and take place at Visit 1. During the Preparatory Sessions:

- a. This visit may be conducted by telemedicine or phone.
- b. Therapists may record all sessions to audio and video. The PTSD+ participant and the CSO participant will be given access to review audio or video recordings from the sessions upon request.

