#### **Baseline Values**

Baseline values are from screening/baseline visit for all measures, except CAPS-5 and C-SSRS. Baseline CAPS-5 will be assessed, during screening (pre-study), no more than 8 weeks before the first experimental session. This allows adequate washout of at least five half-lives of pre-study psychiatric medications and active metabolites, plus one week for stabilization. If CAPS-5 is completed outside of this window for a participant, the PI will consult the CRA and Medical Monitor to determine if the Baseline CAPS should be repeated. For C-SSRS, pre-enrollment scores will be used as a measure of 'lifetime' suicidal ideation and behavior, and preparatory session 2 (visit 2) prior to drug administration will used as 'baseline.' If a subject was not administered the C-SSRS at preparatory session 2 (visit 2), then 'baseline' scores will be visit 3 pre-drug C-SSRS observation.

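### No current-status C-SSRS is scheduled before the drug taper, so suicidality that emerges or recurs during the taper is labelled baseline

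*Protocol*

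**What the plan says.** Participants must stop psychiatric medication to take part, with listed exceptions (Protocol Section 4.2.1). Once eligibility is confirmed at Visit 1, the study physician consults the prescriber to "initiate medication tapering for the PTSD+ participant and the CSO participant, if applicable" (Section 5.2.2). The taper runs between Visits 1 and 2, and Section 4.1 allows up to seven weeks of washout plus one week of stabilization.

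The provisions for the C-SSRS are:

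- Section 5.1.2: "Participants who are discontinuing medication to participate in the study will complete the C-SSRS before and after medication washout". The same section says the instrument has one form for lifetime history and another for current ideation and behavior. It does not say which is used before washout.
- Section 5.2.1, item e: "Qualified study staff will administer the lifetime C-SSRS at baseline to assess suicide risk for both the PTSD+ participant and CSO participant".
- Table 3: ticked at Screening, not at Visit 1, then at Visit 2 with footnote "F = Given after medication washout".
- SAP, Baseline Values: "For C-SSRS, pre-enrollment scores will be used as a measure of 'lifetime' suicidal ideation and behavior", while "preparatory session 2 (visit 2) prior to drug administration will used as 'baseline". If Visit 2 was missed, "then 'baseline' scores will be visit 3 pre-drug C-SSRS observation".
- SAP, C-SSRS analysis: positive ideation, serious ideation and positive behavior are tabulated for each time period. Lifetime serious ideation and behavior are compared with cumulative frequencies over the study.
- SAP, Safety Analyses: treatment-emergent events are those after dosing, plus medical-history diagnoses that worsened during the study.

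**The concern.** Withdrawal of psychiatric medication is a study procedure, and Section 5.1.2 shows that the authors wanted suicidality measured on both sides of it. As scheduled, the two sides are measured on different scales of time: lifetime history before, current state after. The post-washout score is then called baseline, and the fallback at Visit 3 is also post-washout. Harm from the withdrawal would sit in the column that readers take as the condition participants brought to the study.

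The C-SSRS is also out of step with the other measures. The SAP takes baseline for the BDI-II and the other questionnaires from screening, and the baseline CAPS-5 is done during screening, so these precede the taper. Depression and suicidality would be followed from opposite sides of the same withdrawal.

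**Working it through.** The plan states no figure on this point, so the check is to trace what would be recorded and then scale it.

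**Step 1: what each visit yields before any MDMA.** Screening (before the taper): lifetime form. Visit 1 (taper begins): no C-SSRS. Visit 2 (after washout): the score the SAP calls baseline. Visit 3 pre-drug: the fallback, also after washout. No document schedules the current-status form before the taper.

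**Step 2: can these records show what the taper did?** Take three participants who are all positive at Visit 2.

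| Participant | Current state at screening (not scheduled) | Lifetime score | Visit 2 score |
|---|---|---|---|
| A: first-ever ideation, during the taper | none | negative | positive |
| B: past ideation, recurs during the taper | none | positive | positive |
| C: past ideation, still present at screening and at Visit 2 | present | positive | positive |

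A can be identified by setting the lifetime score against Visit 2. B and C have the same record, although only B's ideation returned during the withdrawal. The SAP's lifetime-versus-cumulative comparison does not separate them either: both are positive on the lifetime side, and both are positive on the cumulative side if Visit 2 counts. That comparison is also limited to serious ideation and behavior. Sections 4.2 and 4.2.2 allow a history of suicide attempts, so participants like B are eligible.

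**Step 3: does the adverse event analysis label it?** Psychiatric-status events are collected from Visit 1 (Table 3), and Section 5.2.2, item e, makes new events after enrollment adverse events. The SAP's treatment-emergent definition begins at dosing, with worsened medical-history diagnoses added. A new event during the taper is before dosing and outside that definition. A recurrence might qualify as a worsened diagnosis if the earlier problem was recorded as one. Neither document has a category for events emerging in the taper.

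**Step 4: length of the interval.** Longest case in Section 4.1: 7 + 1 = 8 weeks, for fluoxetine. The next longest washout in Table 7 is 16 days; with the stabilization week, 16 + 7 = 23 days. Most listed drugs are shorter.

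**Step 5: scale.** There are 10 PTSD+ and 10 CSO participants. One case moves a by-role rate by 1/10 = 10 percentage points and the overall rate by 1/20 = 5 points. The number who will taper is not given. Purely as an illustration, assume 2 of 10 PTSD+ participants develop ideation in the taper and recover by Visit 16. The table would read 2/10 = 20% at baseline and 0/10 = 0% at the endpoint, even with no MDMA effect.

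**The case against.** **The cases are not hidden.** A reader might infer that harm from the taper disappears from the study record. The documents do not support that. Psychiatric adverse events are collected from Visit 1 onward, the SAP lists all adverse events and all SAEs, and the C-SSRS is tabulated at each time period, so a positive score at Visit 2 is printed. This stands. What is missing is attribution to the taper and, for a new event, a place in the treatment-emergent tables.

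**The baseline label drives no test.** A reader might also infer that recovery from the taper would be analysed as an MDMA benefit. The SAP plans no change-from-baseline analysis of the C-SSRS, and its one comparison over time uses lifetime, not Visit 2, as the reference. This stands too. The 20% to 0% pattern is a misreading that the table invites, not a planned result.

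**A before-and-after comparison is partly possible.** Section 5.1.2 does not name the pre-washout form, so a site could give the current one. Section 7.2.1 allows the scale as needed and mentions a since-last-visit form; if used at Visit 2, that form would cover the taper. The content of the screening form is not reproduced, so it may say something about recent state. It is therefore too strong to say that no comparison can be made. However, a since-last-visit score still would not separate B from C, and Section 5.2.1 and the SAP name only lifetime for the pre-taper score.

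**Current risk at entry is assessed.** A reader might infer that eligibility rests on a lifetime form alone. It does not: the exclusion criterion also uses psychiatric interview and clinical judgment.

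**Visit 2 is a reasonable baseline.** It is the right reference for change after MDMA and should stay. The fault is the missing reference before the taper.

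**Conclusion.** The point holds as misattribution. The protocol asks for the C-SSRS on both sides of washout, but the schedule and SAP supply no like-for-like pair. Suicidality that emerges or recurs in a study-required taper is labelled baseline. It cannot be separated from the pre-taper state in participants with a positive lifetime history and, if it is a new pre-dose event, it falls outside the treatment-emergent definition.

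Each such case is worth 10 points of a by-role rate or 5 points overall. The number of cases cannot be estimated, because the documents do not say how many participants will taper. The conclusion assumes that sites follow Section 5.2.1 as written and give only the lifetime form at screening. The primary CAPS-5 analysis is unaffected. The change is worth making because safety is part of the overall objective, there is no control arm to show what the taper alone does, and the remedy is cheap.

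**What to change.** 1. Protocol: reconcile Table 3 and Section 5.2.1, item e, with Section 5.1.2, so that the current-status form is recorded with the lifetime form at screening, before any taper.
2. SAP, Baseline Values: keep Visit 2 (or Visit 3 pre-drug) as the pre-MDMA reference and label it post-washout in the tables. State that the screening current-status score is the pre-taper reference.
3. SAP, C-SSRS analysis: for participants who tapered, add a row giving the change from screening current status to Visit 2, reported as on-study, pre-dose ideation or behavior, with the number who tapered as denominator.

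The cost is a few minutes per participant for a second form of an instrument already given at that visit, a short SAP addition and one more table row. No sample size, test or clinical rule changes. If enrollment has passed the point where the form can be added, the Visit 2 label and a count of pre-dose psychiatric adverse events among those who tapered can still be reported.
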